5.5 CONCOMITANT MEDICATION

All medication at study registration, received within the 14 days prior to first drug administration and during the on-treatment period must be documented in the electronic case report forms (e-CRF). The details to be entered for each type of treatment will depend on factors such as relationship to, for example, AEs, underlying disease and symptoms, and will be defined in the study's e-CRF completion guidelines.

5.5.1 Prophylactic Medication

Primary antiemetic prophylaxis is compulsory before all PM060184 dose administrations. Standard treatment according to the American Society of Clinical Oncology (ASCO) guidelines will be administered:

- 5-HT₃ antagonists (ondansetron 8 mg or equivalent).
- Steroids (dexamethasone 8 mg or equivalent).

Oral or i.v. formulations are allowed according to institutional standards.

If necessary, additional antiemetic therapy can be considered in accordance with ASCO guidelines.

5.5.2 Allowed Medications/Therapies

- Therapies for pre-existing and treatment-emergent medical conditions, including pain management.
- Blood products and transfusions, as clinically indicated.
- Approved therapies for bone metastasis (e.g., bisphosphonates, denosumab).
- In case of nausea or vomiting, prophylaxis and/or symptomatic treatment for emesis according to ASCO guidelines.
- Erythropoietin use according to ASCO guidelines.
- Treatment with granulocyte colony-stimulating factor (G-CSF) in the event of grade 4 neutropenia lasting ≥ 3 days, neutropenic sepsis or febrile neutropenia according to ASCO guidelines. Secondary prophylaxis can be considered if it is in the best interest of the patient.
- Megestrol acetate for appetite stimulation.
- Anticoagulant therapy for the treatment or secondary prophylaxis of thromboembolic events.

5.5.3 Prohibited Medications/Therapies

- Concomitant administration of any other antineoplastic therapy.
- Any other investigational agents.
- Immunosuppressive therapies other than corticosteroids.
- Local therapy such as radiation or surgery if the lesion is the only target lesion, unless agreed in advance with the Sponsor.

5.5.4 Drug-drug Interactions

In vitro studies using human liver microsomes have pointed to CYP2C19 and CYP3A4 as the predominant cytochrome enzymes responsible for the hepatic metabolism of PM060184. Therefore, concomitant drugs that induce or inhibit any of these cytochromes to a significant extent should be avoided whenever possible ([Appendix 4](#)).

5.6 DRUG ACCOUNTABILITY

Each study site will keep records to allow a comparison of quantities of drug received and used at each site. The Investigators at each study site will be the person ultimately responsible for drug accountability at the site.

All unused drug supplied by the Sponsor will be properly destroyed at the study site. Documentation of this procedure must be provided to the clinical trial monitor. If the Sponsor agrees, unused drug supplies may be returned to the drug repository.

5.7 TREATMENT COMPLIANCE

The Investigator is responsible for supervising compliance with the instructions described in this study protocol.

6. PLAN OF THE STUDY

6.1 DURATION OF THE STUDY (WHOLE POPULATION)

The total duration of the study will be approximately 36 months.

- **Planned start date (first patient first visit):** 4Q2017.
- **Planned enrollment period:** approximately 20 months.
- **Planned study termination date:** 12 months after the first PM060184 administration of the last evaluable patient treated in the study.

6.2 DURATION OF THE STUDY (PER PATIENT)

Patients will be evaluated at scheduled visits in the following study periods:

- **Screening:** from signature of informed consent to registration (confirmation of eligibility) or screen failure.
- **Pretreatment:** from registration to first dose of study treatment.
- **Treatment:** from the first administration of the study treatment to end of treatment (EOT). EOT is standardly defined as 30 days (\pm 15 days) after the day of last administration of study treatment, unless the patient starts a new antitumor therapy or dies within 30 days of the last dose, in which case the date of administration of this new antitumor therapy or the date of death will be considered the EOT date.
- **Follow-up:** after EOT, patients will be followed for both safety and efficacy.
 - 1) **Safety:** every four weeks until resolution or stabilization of drug-related AEs (if any).
 - 2) **Efficacy:** about every three months until death, refusal to continue participating in the study, or study termination (clinical cutoff), whichever occurs first.

Subsequent off-study antitumor therapies should be provided until death, refusal and/or clinical cutoff (whichever occurs first).

Note: patients without disease progression who discontinue treatment due to a drug-related AE must be followed both for the AE and for efficacy.

Patients will be considered to be **on-study** from the signature of the informed consent form (ICF) to the end of the follow-up period (or screening failure). Investigators can appraise potential study candidates in a pre-screening period but only perform study-specific screening assessments after the patient formally consents. Patients will be considered to be **on-treatment** from the date of first dose until EOT.

Patients may withdraw their consent at any time; if consent to study participation is withdrawn, no further study activities will be conducted on them (Section [6.3.3](#)). If consent only to receive the study treatment is withdrawn, treatment will be stopped and other study procedures performed as normal (see [7.5](#) and [7.6](#) below).

6.3 DISCONTINUATIONS

6.3.1 Treatment Discontinuation

Treatment discontinuation occurs when an enrolled patient ceases to receive the study medication, regardless of the circumstances. By convention, the date of end of treatment will be 30 days (\pm 15 days) after the date of the last administration of study drug, unless the patient starts a new antitumor therapy or dies within those 30 days, in which case the

date of administration of this new therapy or the date of death will be considered the date of end of treatment.

The primary reason for any discontinuation will be recorded on the patient's e-CRF.

If a patient discontinues treatment, every effort should be made to complete the scheduled assessments.

6.3.2 Reasons For Treatment Discontinuation

Patients will receive study treatment while it is considered to be in their best interest or until study termination. Specifically, treatment will continue until:

- Disease progression.
- Unacceptable toxicity (including any toxicity leading to the need for a third dose reduction or severe hypersensitivity reactions, except in the case of obvious clinical benefit, in which event the patient could be allowed to remain on treatment once agreed with the Sponsor).
- Patient refusal to receive further study treatment and/or non-compliance with study requirements.
- Intercurrent serious illness.
- Pregnancy.
- Investigator's decision.
- Protocol deviation with an effect on the risk/benefit ratio of the clinical trial.
- PM060184 treatment delay > 15 days from the due date (except in case of clear clinical benefit and with the Sponsor's approval).
- Clinical cutoff. Patients who have not progressed at these time points could be treated in a compassionate use program (according to country regulations).

Patients who are withdrawn for any reasons must not be re-treated in the context of this study at any time. For follow-up activities, please refer to Section [7.6](#).

6.3.3 Study Discontinuation

Study discontinuation occurs when an enrolled patient ceases to participate in the study, regardless of the reason. Patients have the right to withdraw consent at any time; if this is the case, no further study procedures should be performed. The date and reason for study discontinuation will be clearly documented on the patient's e-CRF.

6.3.4 Replacement of Patients

Patients must be replaced if they are considered not evaluable for efficacy for the primary endpoint (PFS3), i.e., if they are withdrawn from the study due to significant clinical deterioration of unknown reason, hypersensitivity reactions, unrelated AEs without any tumor assessments after the start of study treatment, if they receive less than one complete treatment cycle (at least two PM060184 dose administrations over two cycles unless treatment discontinuation was due to unmanageable toxicity), or do not have the disease assessment at Week 12 (except in the case of treatment discontinuation/death due to a treatment-related AE, symptomatic deterioration due to the disease, clinical progression, PD or death due to malignant disease).

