8. STUDY EVALUATIONS

8.1 EFFICACY

Patients will be evaluable for efficacy if they receive at least one complete treatment cycle (or two PM060184 dose administrations over two cycles) and have, at least, one disease assessment at Week 6 and another one at Week 12.

In addition, any patient who presents disease progression, symptomatic deterioration due to the disease or clinical progression, dies due to malignant disease, discontinues treatment due to unmanageable toxicity, or dies or discontinues treatment due to a treatment-related AE before evaluation of the response at Week 12 will also be considered evaluable for the primary endpoint and classified as a non-responder.

Patients who have no disease assessment at Week 6 but remain on treatment and are assessed at Week 12 (or later, and with no evidence of disease progression) will be considered evaluable for efficacy.

Patients who refuse further treatment before Week 12 due to reasons other than related AEs not considered unmanageable toxicity will be replaced.

A futility analysis will be performed once the first 24 evaluable patients complete the Week 12 (\pm 5 days) tumor assessment; progress; die due to PD; or discontinue treatment due to unmanageable toxicity (whichever occurs first). If seven patients or more achieve PFS3, then 36 additional patients will be recruited (second stage).

Tumor assessment will be measured using RECIST v.1.1 ([17](#)).

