9.3 SAMPLE SIZE

Patients will be treated with PM060184 to test the null hypothesis (H0) that 30% or less patients are alive and free of progression at twelve weeks (PFS3) according to RECIST v.1.1 ($p \leq 0.30$) versus the alternative hypothesis (H1) that 50% or more patients are alive and free of progression at 12 weeks according to the aforementioned criteria ($p \geq 0.50$). The variance of the standardized test is based on the null hypothesis. The type I error (alpha) associated with this one-sided test is 0.025 and the type II error (beta) is 0.1; hence, statistical power is 90%.

Sixty evaluable patients are necessary to test the hypothesis. A futility analysis using O'Brien-Fleming boundaries is planned when 24 patients can be evaluated (first stage). If there are seven or more patients achieving PFS3 in the first stage then the trial will proceed to a second stage and a total of 60 patients will be recruited.

If at least 25 of 60 evaluable patients are alive and free of progression at 12 weeks then the null hypothesis can be rejected and PM060184 considered active and deserving potential development in this setting.

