6.2.2. Secondary Endpoints

Time-to-event variables (DOR, PFS and OS) and their fixed time estimates will be analyzed according to the Kaplan-Meier method. Kaplan-Meier curves will be plotted.

For categorical variables, comparisons will be carried out by a Fisher exact test and a multivariate analysis by logistic regression. For time-to-event variables, comparisons will be carried out by a log-rank test and by a Cox regression analysis. No formal conclusions will be expected on these grounds. Exploratory comparisons will be performed at a 0.05 level.

If appropriate, exploratory multivariate models (main effects or including interaction terms) will include all prognostic factors/covariates widely reported and recognized by oncologists: age, age at diagnosis, baseline ECOG PS (Eastern Cooperative Oncology Group Performance Status), stage at diagnosis, Tumor primary location: right vs left side tumors; sites of metastasis; visceral vs non visceral, body mass index (BMI), body surface area (BSA), time from diagnosis to first infusion, time from diagnostic of metastatic disease to first infusion, prior advanced treatment lines, last prior therapy PFS, prior oxaliplatin exposure, KRAS status, BRAF-like expression, any relevant concomitant medication at baseline; EORTC-QLQ-C30 and QLQ-CPN20 score at baseline and other prognostic/predictive factors determined by the oncologist. The total number of variables included in the final model will always be in accordance with the number of events and the sample size, thus, whenever possible, no more than one variable per ten events will be included. The parameter estimates, hazard ratios and p-values of the variables retained in the model will be presented.

A sensitivity analysis for PFS including all treated patients will be performed. Event will be defined as progression or death irrespective of the subsequent therapies received for this analysis.

Waterfall plots will be used to describe the best variation of the sum of target lesions during treatment. Questionnaires scores over time will be described by time series charts, if appropriate.

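### Treated patients withdrawn before Week 12 for deterioration of unknown cause are replaced, although the same decline attributed to the disease is a PFS3 failure, and no PFS3 analysis adds them back

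*Protocol*

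**What the plan says.** Three places in the current text make a patient non-evaluable for PFS3, to be replaced, if "withdrawn from the study due to significant clinical deterioration of unknown reason": the protocol synopsis (replacement of patients), Protocol 6.3.4 and SAP 4.

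The lists of patients who are evaluable and scored as non-responders (synopsis efficacy evaluations, Protocol 8.1, SAP 4) include documented progression, "symptomatic deterioration due to the disease or clinical progression, dies due to malignant disease", unmanageable toxicity, and death or discontinuation from a treatment-related AE. Deterioration of unknown cause is not among them.

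PFS3 is analysed in the evaluable set only (SAP 4.2). Both decision rules, 7 of 24 and 25 of 60, count evaluable patients. SAP 11.3.1 scores short follow-up as PFS3 = No, but only for patients already classed as evaluable. For all treated patients the SAP says "A sensitivity analysis for PFS including all treated patients will be performed". It plans no such analysis for PFS3.

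**The concern.** Two treated patients may decline in the same way before Week 12. One is recorded as a disease-related decline and is a failure. The other is recorded as a decline of unknown cause, leaves the denominator, and is replaced by a new patient. What separates them is a judgement made after the decline, in an open-label single-arm trial, and the documents give no criteria for it. SAP Table 10.2.1 has no category for either label.

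The exclusion is post-baseline and plausibly related to the outcome. Eligible patients have advanced disease that progressed on their last treatment. A patient who leaves in decline without a Week-12 scan has not been shown to meet the endpoint. If such patients fail more often than the rest, replacement raises the PFS3 estimate and the chance of a wrong go decision at both looks.

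**Working it through.** **Who is affected.** The patient must have no documented progression, no disease attribution, no death from malignant disease, no toxicity or treatment-related ground for non-response, and no Week-12 scan. In 6.3.4 the qualifier about having no tumor assessment since starting treatment may attach to unrelated AEs only or to all three grounds listed there. On the wider reading, only patients with no post-baseline scan are replaced on this ground.

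**The plan's own figure.** Inputs from Protocol 9.3 are p0 = 0.30 and p1 = 0.50, with error rates given as "The type I error (alpha) associated with this one-sided test is 0.025 and the type II error (beta) is 0.1", and "The variance of the standardized test is based on the null hypothesis".

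- N = (1.96·√(0.3·0.7) + 1.2816·√(0.5·0.5))² / 0.2² = 59.2, so 60. This agrees with "Sixty evaluable patients are necessary to test the hypothesis".
- Critical count = 18 + 1.96·√(60·0.3·0.7) = 24.96, so 25.
- Exact binomial for 25/60: alpha 0.0362, power 0.922.
- Exact two-stage, Σ over x ≥ 7 of P(Bin(24,p) = x)·P(Bin(36,p) ≥ 25 − x): 0.0355 at p = 0.30 and 0.918 at p = 0.50.

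N and the cutoff reproduce by normal approximation. The exact error exceeds 0.025 before anyone is replaced. A cutoff of 26/60 would give alpha 0.0196 and power 0.877.

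**Effect of replacement.** Let d be the share of treated patients replaced on this ground and f the proportion of them who would fail PFS3. Both are assumptions, since the documents give neither. If the true rate in all treated patients is 0.30, the rate among evaluable patients is

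q = (0.30 − d(1 − f)) / (1 − d).

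Then q > 0.30 exactly when 1 − f < 0.30, that is, f > 0.70. Below that, replacement makes the rule conservative.

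If all would fail (f = 1), q = 0.30/(1 − d):

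| d | q | P(≥ 7/24) | two-stage false go |
|---|---|---|---|
| 0 | 0.300 | 0.611 | 0.0355 |
| 2% | 0.306 | 0.636 | 0.0446 |
| 5% | 0.316 | 0.674 | 0.0626 |
| 10% | 0.333 | 0.737 | 0.1081 |

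If 80% would fail:

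- d = 5%: q = (0.30 − 0.05·0.2)/0.95 = 0.305, false go 0.0432.
- d = 10%: q = (0.30 − 0.10·0.2)/0.90 = 0.311, false go 0.0533.

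**A trial that just passes.** With 25/60 the exact one-sided p is 0.0362. Adding back one replaced patient as a failure gives 25/61 = 41.0%, p = 0.0443. Adding three gives 25/63 = 39.7%, p = 0.0644.

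**The case against.** The plan has more protection than the replacement clause suggests.

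- **Scans.** A reader might infer that no scan is required once such a patient stops. Footnote 12 of the assessment schedule and Protocol 7.6 require the Week-12 evaluation in every patient without progression, and the footnote names those off treatment. Under Protocol 6.2, stopping treatment alone leaves other study procedures in place. Progression documented before Week 12 makes the patient an evaluable failure. This narrows the gap. It does not close it, because the clause concerns patients withdrawn from the study, whom the scan may never reach.
- **Visibility.** A reader might infer that these patients vanish from the report. They do not. Table 10.1.1 gives treated and evaluable counts, Listing 10.1.4 gives the reason for each non-evaluable patient, and Listing 10.2.2 covers discontinuations other than progression. Table 11.3.7 reports 3-month PFS in all treated patients. That Kaplan-Meier estimate may censor them, however, and it is not set against the 25-of-60 rule. A reader could recompute 25/(60 + k), but the plan does not.
- **Size.** The frequency is unknown and may be near zero. That these patients are mostly progressors is an inference. The 30% null is also stated for a rule on evaluable patients, with no source given, so applying it to all treated patients is an assumption.
- **Purpose.** The rule is prespecified and essentially the same in both documents, and a positive result only supports possible further development.

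These points limit the size and severity. They do not explain why the same decline should be scored differently according to its label.

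**Conclusion.** The concern holds in a limited form. An outcome-related exclusion feeds both decision points, and no PFS3 analysis reverses it. Under the assumptions above, it adds at most 0.9, 2.7 or 7.3 percentage points to a 3.55% false-go probability for d = 2%, 5% or 10%, when every replaced patient would fail. At an 80% failure rate it adds 0.8 points (d = 5%) or 1.8 points (d = 10%). At 70% it adds nothing.

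Two stronger readings are not supported. One is that the trial's false-positive rate is about 11%: that is the upper end of an assumed range, not a figure the documents yield. The other is that replacement explains why the error exceeds 0.025: the step from 0.025 to 0.0355 comes from the 25/60 cutoff.

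This should be fixed. Because the affected number is unknown and possibly small, it does not invalidate the design.

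**What to change.** 1. Delete deterioration of unknown cause as a ground for replacement in the synopsis, Protocol 6.3.4 and SAP 4.
2. Add clinical deterioration of unknown cause before Week 12 to the non-responder lists in the synopsis efficacy evaluations, Protocol 8.1 and SAP 4. Such patients are evaluable with PFS3 = No unless a Week-12 scan shows no progression.
3. Add the same case to the exceptions to the missing-Week-12-assessment ground in the synopsis, 6.3.4 and SAP 4. Without this, step 1 changes little, because these patients would still be replaced for lacking that assessment.
4. Limit the change to unknown-cause deterioration, so that it does not conflict with the unrelated-AE ground, which stays as written.
5. Add a PFS3 sensitivity analysis in all treated patients, counting anyone without documented progression-free status at Week 12 as a failure.

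The cost is wording in two documents and one extra table. The PFS3 rate may be slightly lower. For unknown-cause declines counted within a fixed 60, the operating characteristics return to those of the planned rule: two-stage alpha 0.0355 and power 0.918.

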Patients must be replaced if they are considered not evaluable for efficacy for the primary endpoint (PFS3), i.e., if they are withdrawn from the study due to significant clinical deterioration of unknown reason, hypersensitivity reactions, unrelated AEs without any tumor assessments after the start of study treatment, if they refuse further treatment before Week 12 due to reasons other than related AEs not considered unmanageable toxicity, if they receive less than one complete treatment cycle (at least two PM060184 dose administrations over two cycles unless treatment discontinuation was due to unmanageable toxicity), or do not have the disease assessment at Week 12 (except in the cases outlined above).

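### A hypersensitivity stop related to PM060184 before Week 12 can meet both the PFS3 failure rule and the mandatory replacement rule, and neither document says which governs

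*Protocol*

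**What the plan says.** **Failure rule.** Protocol 8.1 lists the patients who count as evaluable non-responders although they have no Week 12 evaluation. The list ends with a patient who "or dies or discontinues treatment due to a treatment-related AE before evaluation of the response at Week 12". The synopsis (efficacy evaluations) and the SAP section 4 definition of the efficacy set repeat it.

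**Replacement rule.** Protocol 6.3.4 makes replacement mandatory for patients not evaluable for PFS3, and the first grounds it names are: "withdrawn from the study due to significant clinical deterioration of unknown reason, hypersensitivity reactions, unrelated AEs without any tumor assessments". The assessments meant are those made once treatment has begun. The synopsis has the same list. SAP section 4 repeats it after its set definitions: "hypersensitivity reactions, unrelated AEs without any tumor assessments after the start of study treatment".

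**Further grounds in the same lists.** A patient with less than one complete cycle is replaced unless the stop was for unmanageable toxicity, a term that neither document defines. A patient without the Week 12 assessment is also replaced. In the protocol, the exception for treatment-related AEs is attached to this last ground only. The SAP puts a back-reference to the cases already outlined in the same position.

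**Classification.** Protocol 6.3.2 places severe hypersensitivity under toxicity: "Unacceptable toxicity (including any toxicity leading to the need for a third dose reduction or severe hypersensitivity reactions".

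**The concern.** A patient who has to stop PM060184 because of a reaction to it has stopped for a treatment-related AE. Under 8.1 that is a PFS3 failure. Under 6.3.4 and SAP section 4 the same patient can be removed and the slot given to someone who may succeed. No passage explains why this one drug-related toxicity should be handled differently from the others, and no order of precedence is given.

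The trial is open-label and single-arm, and it is decided by a count. If such a case arises, someone must choose a rule with the patient's outcome already known. Choosing replacement can only help the result on average, at both the futility look and the final analysis.

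**Working it through.** **1. Do the two rules overlap?** Take a patient with a Cycle 1 reaction judged related to PM060184 who stops before the Week 6 scan.

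| Rule | Condition | Met? | Result |
|---|---|---|---|
| Protocol 8.1; SAP 4 efficacy set | Stops for a treatment-related AE before Week 12 | Yes | Evaluable, non-responder |
| Protocol 6.3.4; SAP 4 replacement list | Withdrawn for hypersensitivity | Yes | Not evaluable, replaced |
| Same lists, under-one-cycle ground | Less than one complete cycle, not unmanageable toxicity | Yes after a single dose, unless the stop is called unmanageable toxicity | Not evaluable, replaced |

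The next item in the replacement list is restricted to unrelated AEs, but the hypersensitivity item carries no such word. If the phrase about having no tumor assessment is read as governing the whole list, the overlap narrows to patients without a post-baseline scan. This patient is still in it.

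**2. The plan's design (Protocol 9.3).** Inputs: p0 = 0.30, p1 = 0.50, power 90%, null variance for the test, and "The type I error (alpha) associated with this one-sided test is 0.025".

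- n = [(1.960·√(0.30·0.70) + 1.282·√(0.50·0.50)) / 0.20]² = 59.2, so 60, as stated.
- Critical count = 60·(0.30 + 1.960·√(0.21/60)) = 24.96, so 25, as stated.

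Exact two-stage probability of declaring activity (at least 7/24, then at least 25/60):

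P(q) = Σ from x = 7 to 24 of Bin(x; 24, q) · Pr[Bin(36, q) ≥ 25 − x]

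This gives P(0.30) = 0.0355 and P(0.50) = 0.918. That 0.0355 exceeds the nominal 0.025 is a separate matter. Here it serves only as the baseline.

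**3. Effect of replacement.** Let h be the share of treated patients who stop before Week 12 for a related hypersensitivity reaction and are replaced. The documents give no value, so h is an assumption. Let p be the PFS3 rate in all treated patients with these stops counted as failures. The rate among those analysed is then q = p/(1 − h).

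| h | q at p = 0.30 | P(q) | Stage 1 stop | P(q) at p = 0.40 |
|---|---|---|---|---|
| 0 | 0.3000 | 0.0355 | 0.389 | 0.4382 |
| 0.5% | 0.3015 | 0.0376 | 0.382 | 0.4508 |
| 1% | 0.3030 | 0.0398 | 0.376 | 0.4635 |
| 1.7% (1/60) | 0.3051 | 0.0430 | 0.368 | 0.4807 |
| 3% | 0.3093 | 0.0500 | 0.351 | 0.5158 |

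**4. One patient at the margin.** With 24/60 including one such failure, replacement reaches 25/60 only if the new patient succeeds, with probability 0.30 to 0.50 across the design rates. In the other direction, 25/60 (exact one-sided p = 0.036 against 0.30) becomes 25/61 (p = 0.044) when one replaced failure is put back.

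**The case against.** Several points on the other side have weight.

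- **Relatedness.** A reader might infer that every hypersensitivity withdrawal is a drug failure. The documents do not say so. 8.1 does not name hypersensitivity, and relatedness is the investigator's judgement (8.4.7). Patients also receive compulsory antiemetics and steroids (5.5.1) and, where appropriate, contrast CT (7.4), so some reactions may be to something else. Replacing those patients does not conflict with the treatment-related AE rule. This limits the point to related reactions.
- **Different triggers.** 6.3.4 speaks of leaving the study and 8.1 of stopping treatment, and 6.3.1 and 6.3.3 define these separately. Patients who stop without progression should still have the Week 12 scan (7.6). But 6.3.2 uses the word for withdrawal within the treatment-stopping section, and nothing says the difference decides the scoring.
- **A deliberate carve-out.** A named item could be meant to override a general rule. That is possible, but neither document says so, and SAP section 4 contains both rules.
- **Size.** The clinical summary (1.2.2) does not mention hypersensitivity, and known hypersensitivity to the class or excipient is excluded (4.2), so the rate may be near zero. If the 30% null is defined in evaluable patients, as 9.3 can be read, the figure stays at 3.55%. Both points stand.
- **Transparency.** SAP Listing 10.1.4 gives reasons for non-evaluability, so a reader could put replaced patients back as failures. The planned all-treated sensitivity analysis concerns PFS, not PFS3, and does not make a hypersensitivity stop an event. This mitigates the problem but does not settle the primary analysis.

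**Conclusion.** The conflict is real and stands in both documents, but it is narrow. It covers hypersensitivity stops before Week 12 judged related to PM060184, most clearly those before any post-baseline scan. Replacement removes a certain failure, so the bias has one direction on average.

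The size is modest: from 3.55% to between 3.8% and 5.0% for assumed rates of 0.5% to 3%, and only with the null set in all treated patients. Two stronger readings are not supported. One is that the trial's type I error is inflated by a known amount: no rate is given, and the effect depends on which population the null refers to. The other is that one replacement turns 24/60 into 25/60: that needs the new patient to succeed.

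The defect does not depend on the rate. A single event would force an unspecified choice on the primary endpoint. It should be corrected as a clarification of endpoint scoring.

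**What to change.** This concerns endpoint scoring only, not patient management. In the synopsis, Protocol 6.3.4 and the SAP section 4 replacement paragraph:

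1. Limit the hypersensitivity ground to reactions judged unrelated to PM060184.
2. In the clause on less than one complete cycle, extend the exception from unmanageable toxicity to discontinuation or death due to any treatment-related AE.

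The second change is needed. If the hypersensitivity item were simply deleted, a patient stopping after one dose would still be replaceable under the one-cycle ground. With both changes, a related first-dose reaction is scored as a non-responder and not replaced, in line with 8.1 and the SAP efficacy set.

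Cost: a few words in three places, and a PFS3 rate that may be slightly less favourable.
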